4.0 Abstract

Title: Post-Marketing Surveillance of Humira® in Korean Pediatric CD Patients under the “New-Drug Re-examination”
Rationale and Background: This non-interventional, observational study will be conducted in compliance with the New Drug Re-examination Guideline in Korea
Research Question and Objectives: To evaluate the safety profile of Humira® for Pediatric CD patients in normal medical practice: (1) Serious adverse event•adverse drug reaction (2) Unexpected adverse event•adverse drug reaction (3) Already known adverse drug reaction (4) Non-serious adverse drug reaction (5) Adverse events resulting from drug misuse, drug abuse or drug interaction (6) Other information related to the product’s safety and effectiveness (including the influence to the laboratory value)
Study Design: Post-Marketing Surveillance
Population: Pediatric CD patients who have been prescribed Humira® by the treating physician
Variables: Demographics, Medical History, PPD Skin Test, Chest X-ray, Interferon Gamma Release Assay, Concomitant Medication, Safety, PCDAI score (CDAI score if it is evaluated)
Data Sources: paper Case Report Form
Study Size: 141 patients
Study Duration : 12 Sep 2013 ~ 11 Sep 2017
Data Analysis: (1) The safety analysis data set : all subjects who have received at least one dose of Humira® during the study and have been followed up for the safety information (2) The effectiveness analysis data set: 
Effectiveness of Humira® induction therapy: all subjects who have been administered Humira® and received Humira® for 4 weeks including induction period (± 1 week) and for whom effectiveness evaluation parameters have been recorded.Maintenance effectiveness of Humira®: all subjects who have been administered Humira® and received Humira® for 6 months (± 4 weeks) and for whom effectiveness evaluation parameters have been recorded.
Milestones: (1) Start of Data collection : 1Q 2015 (2) End of Data collection : 3Q 2017 (3) Final Report of Study Results : 4Q 2017

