8.0 Research Question and Objectives

The objective of this surveillance is to evaluate the following items regarding the safety profile of Humira® for Pediatric CD patients in normal medical practice:

- (1) Serious adverse event & adverse drug reaction
- (2) Unexpected adverse event & adverse drug reaction
- (3) Already known adverse drug reaction
- (4) Non-serious adverse drug reaction
- (5) Adverse events profile resulting from drug misuse, drug abuse or drug interaction
- (6) Other information related to the product's safety and effectiveness (including the influence to the laboratory value)

The hypothesis of this study is that Humira® will present a safety profile consistent with that seen in the phase 3 clinical studies and will be efficacious in Korean Pediatric CD patients.

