Regardless of results of causality assessment, presence of adverse event(s), type of adverse event(s), onset, end date, severity, causality assessment by physician on the adverse event(s), action taken, outcome will be captured, during the study, from the first administration to the surveillance period (from informed consent to up to 70 days following the last administration of Humira®) (Section 11.0 Management and Reporting of Complaints).

Effectiveness

From the patients treated with Humira®, the effectiveness data (i.e. PCDAI score) at previous times before Humira® treatment, at 4 weeks (visit window: ± 1 week) and at 6 months (visit window: ± 4 weeks) post-treatment will be collected. (CDAI score will be collected as well, if possible.)

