For induction effectiveness of Humira®, the effectiveness analysis data set will include all subjects who have been administered Humira® and prescribed Humira® for 4 weeks including induction period (± 1 week) and for whom effectiveness evaluation parameters have been recorded. And for maintenance effectiveness of Humira®, effectiveness analysis data set will include all subjects who have been administered Humira® and prescribed Humira® for 6 months (± 4 weeks) and for whom effectiveness evaluation parameters have been recorded. The subjects whose effectiveness evaluation was not properly conducted because their data from evaluation parameters were missing or they discontinued administration prior to the effectiveness evaluation will be excluded from the evaluation.

Safety Analysis

The adverse events will be coded by MedDRA dictionary. The number and percentage of subjects reporting any serious adverse events/adverse drug reactions will be tabulated overall and by MedDRA 17.0 or more recent version, in preferred term. The number and percentage of subjects reporting unexpected (unlabeled) adverse drug reactions will be tabulated in a similar fashion.

To investigate the factors affecting the safety, the number and percentage of subjects reporting adverse events will also be classified by various background factors (e.g., demographic factors, treatment factors such as medical history, dosing and administration, concomitant medications, beginning of administration before/after the registration date, etc.) and tabulated. If the incidence of adverse events in the subjects who began the administration before/after the registration date has statistical significance, it will be presented as a separate item. In addition, if there are patients who have already been

administered Humira® when participating in the surveillance, their adverse events from the first administration of Humira® to the inclusion will be presented in a separate table. If data from special patient groups are collected, they will be extracted and tabulated separately for adverse events/adverse drug reactions.

Effectiveness Analysis

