11.1 Medical Complaints

11.1.1 Adverse Event Definition and Serious Adverse Event Categories

An adverse event (AE) is defined as any untoward medical occurrence in a patient, which does not necessarily have a causal relationship with their treatment. An adverse event can therefore be any unfavorable and unintended sign (including an abnormal laboratory finding), symptom, or disease temporally associated with the use of a medicinal product, whether or not the event is considered causally related to the use of the product.

Such an event can result from use of the drug as stipulated in the labeling, as well as from accidental or intentional overdose, drug abuse, or drug withdrawal. Any worsening of a pre-existing condition or illness is considered an adverse event.

If an adverse event meets any of the following criteria, it is considered a serious adverse event (SAE):

Death of Patient:	An event that results in the death of a patient.
Life-Threatening:	An event that, in the opinion of the investigator, would have resulted in immediate fatality if medical intervention had not been taken. This does not include an event that would have been fatal if it had occurred in a more severe form.□
Hospitalization:	An event that results in an admission to the hospital for any length of time. This does not include an emergency room visit or admission to an outpatient facility.
Prolongation of Hospitalization:	An event that occurs while the study patient is hospitalized and prolongs the patient's hospital stay.
Congenital Anomaly:	An anomaly detected at or after birth, or any anomaly that results in fetal loss.
Persistent or Significant Disability/Incapacity:	An event that results in a condition that substantially interferes with the activities of daily living of a study patient. Disability is not intended to include experiences of relatively minor medical significance such as headache, nausea, vomiting, diarrhea, influenza, and accidental trauma (e.g., sprained ankle).
Important Medical Event Requiring Medical or Surgical Intervention to Prevent Serious Outcome:	An important medical event that may not be immediately life-threatening or result in death or hospitalization, but based on medical judgment may jeopardize the patient and may require medical or surgical intervention to prevent any of the outcomes listed above (i.e., death of patient, life threatening, hospitalization, prolongation of hospitalization, congenital anomaly, or persistent or significant

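### Objective (2) covers unexpected adverse events as well as reactions, but section 9.7 tabulates only unexpected reactions, so no planned output identifies unexpected events judged unrelated

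*Combined protocol and SAP*

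**What the plan says.** Objective (2) in section 8.0 reads "Unexpected adverse event & adverse drug reaction". The abstract (4.0) gives the same two-part scope. In both places objectives (1) and (2) name events and reactions, while (3) and (4) name reactions only.

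Section 9.3 collects the data that this scope needs: "Regardless of results of causality assessment, presence of adverse event(s), type of adverse event(s), onset, end date, severity, causality assessment by physician". Section 11.1.1 defines an adverse event as an occurrence that "does not necessarily have a causal relationship with their treatment". Section 11.1.3 gives four causality categories: Probable, Possible, Probably Not and Not Related.

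The Safety Analysis in 9.7 says of serious events: "The number and percentage of subjects reporting any serious adverse events/adverse drug reactions will be tabulated overall", with MedDRA preferred terms. The next sentence turns to unexpected ones: "The number and percentage of subjects reporting unexpected (unlabeled) adverse drug reactions will be tabulated in a similar fashion".

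The other safety outputs in 9.7 are adverse events by background factor, a separate table of events before inclusion for patients already on treatment, separate tables for special patient groups, and the overall adverse event incidence with a 95% CI.

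**The concern.** An adverse drug reaction is, in ordinary use, an adverse event for which a causal link to the drug has not been ruled out. A table of unexpected reactions is therefore a table of unexpected events that has passed through the physician's causality assessment. The objective does not ask for that filter, and the collection rule in 9.3 expressly avoids it.

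Section 7.0 gives comparison of the safety data with the product label as the rationale for the surveillance. An unlabelled event is exactly what that comparison should bring out. If the physician attributes it to Crohn's disease, to another illness or to a concomitant drug, the plan as written contains no place where the reader of the report would see it identified as unlabelled. With one treated cohort and no control group, the reader also has no internal comparison against which to check that attribution.

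**Working it through.** **1. The plan's own figure.** Section 9.7 takes an event rate of 0.5% and 600 subjects, so the Poisson mean is 600 × 0.005 = 3 and P(at least one) = 1 − exp(−3) = 0.9502. This reproduces (exact binomial: 0.9506). At the current size of 141 the mean is 141 × 0.005 = 0.705 and the probability is 1 − exp(−0.705) = 0.506. The mismatch does not depend on these figures; they supply the formula and one of the rates used in step 3.

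**2. Where an unexpected event judged unrelated would appear.**

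| Output in 9.7 | Includes it? | Shown by preferred term? | Marked as unexpected? |
|---|---|---|---|
| Serious events/reactions | Only if serious | Yes | No |
| Unexpected reactions | No, on the ordinary meaning of reaction | – | – |
| Events by background factor | Yes | Not specified | No |
| Events before inclusion | Only for patients already on treatment | Not specified | No |
| Special patient groups | Only for those groups | Not specified | No |
| Overall incidence with 95% CI | Yes | Not specified | No |

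No row both includes the event and marks it as unexpected. For a non-serious event, no row specifies a preferred-term listing either. The words about similar fashion in the unexpected-reaction sentence carry over the layout of the preceding sentence (number, percentage, preferred term). They do not change the subject of the sentence, which is reactions. The serious-event and special-group sentences name both events and reactions, so the narrower wording for unexpected ones is a real difference in the text.

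**3. Illustration of size.** Let p be the true rate of a non-serious unlabelled event, u the share of its cases judged unrelated, and n = 141 (section 9.5). The chance that a reaction-only table has at least one entry is 1 − exp(−n·p·(1 − u)). Setting u = 0 gives the all-causality table. The documents give no value for u, and 2% and 1% are assumed rates; 0.5% is the plan's own.

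| p | n·p | u = 0 | u = 25% | u = 50% | u = 70% |
|---|---|---|---|---|---|
| 2% | 2.82 | 0.940 | 0.879 | 0.756 | 0.571 |
| 1% | 1.41 | 0.756 | 0.653 | 0.506 | 0.345 |
| 0.5% | 0.705 | 0.506 | 0.411 | 0.297 | 0.191 |

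For example, at p = 2% and u = 70%: 2.82 × 0.30 = 0.846, and 1 − exp(−0.846) = 0.571.

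**The case against.** The strongest reply is that little is hidden. All events stay in the database. Serious ones appear by name in the serious-event table whatever their causality. Every event counts in the overall incidence and the background-factor tables, and section 7.0 promises a comparison of safety data with the label that is not restricted to reactions. The missing table could also be added at reporting. This stands as a limit on the point: a reader might infer that unexpected events judged unrelated disappear from the study report, and the documents do not support that. It does not close the gap. The comparison in 7.0 names no table or rule, and no listed output separates labelled from unlabelled events.

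A second reply is that the strength of the filter is unknown. The documents never say which of the four categories in 11.1.3 make an event a reaction. If only Not Related is excluded, the filter is weaker than if Probably Not is excluded too. This is correct, and it means the reaction table itself cannot be reproduced from the plan.

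A third reply concerns the illustration. The values of u have no source. The drop applies in full only if all cases are non-serious, since serious cases remain visible elsewhere. The safety set may be smaller than 141, because it requires follow-up safety information. And one entry in a table is not a detected signal: an all-causality table in an uncontrolled cohort also collects background illness, and 11.1.1 counts worsening of a pre-existing condition as an adverse event. All of this stands, so the probabilities should be read as illustrations of direction and scale.

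It is also tempting to argue that physicians' causality judgement is especially unreliable for events not yet on the label. Nothing in the documents supports that, and the point does not need it.

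**Conclusion.** The point holds as a mismatch between an objective and its analysis. Sections 4.0 and 8.0 ask for unexpected events and unexpected reactions, 9.3 collects what is needed for both, and 9.7 reports only the reactions. The gap is complete in one respect (nothing specified marks an unexpected event judged unrelated as unexpected) and partial in another (only the non-serious ones also lack a preferred-term listing).

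The conclusion rests on the ordinary meaning of adverse drug reaction, under which at least Not Related events fall outside it. The loss of visibility cannot be estimated from the documents: in the illustration it is nil if no case is judged unrelated and grows with that share. No sample size, data collection item or planned estimate is affected. It should still be corrected before the final analysis, because a stated objective is only partly reported and the correction is small.

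**What to change.** Change the sentence on unexpected reactions in 9.7 so that it calls for the number and percentage of subjects with (a) unexpected (unlabelled) adverse events regardless of causality and (b) unexpected (unlabelled) adverse drug reactions, in adjacent columns, overall and by MedDRA preferred term. This matches the serious-event sentence before it.

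Add one sentence stating which of the four causality categories in 11.1.3 count as an adverse drug reaction, and in particular where Probably Not falls. Without it, column (b) is not reproducible.

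The cost is two sentences, one extra column and some classification work. Expectedness is not among the items listed in 9.3, so every coded event, not only the reactions, must be checked against the label. No new data need be collected from sites. The all-causality column will include background illness, so it should be read beside the reaction column and not as a list of drug effects.

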7.0 Rationale and Background

Rationale

This surveillance will be conducted in compliance with the New Drug Re-examination Guideline in Korea and this protocol is written in accordance with the guideline. Safety data of this study will be compared to product label claim for evaluation of the consistency of the safety profile in the real word setting.

Background

Approximately 25% of IBD patients are diagnosed as children, and the IBD characteristics of pediatric patients differ from those of adults as outlined below.¹⁻³ A recent single center study showed that the incidence of pediatric IBD has been rapidly increasing in Korea in recent years.⁴ In this study, relevant family history was less prevalent and phenotypic expression differed from what was seen in Western countries.

Children with Crohn's disease can experience abdominal pain, intestinal obstruction and strictures, fistulas, abscesses, perianal disease, adverse events of treatment such as corticosteroids and surgery, and nutritional complications. A major difference between adult and pediatric CD is an impact of malnutrition. It can lead to delayed puberty and growth impairment which result in significant psychosocial complications.⁵⁻⁸ At first, the goal of treatment of CD for children is to induce and maintain clinical remission. Restoration and/or preservation of normal growth and pubertal development are additional therapeutic goals in children with CD.⁹

The first line conventional therapy for mild patients includes 5-aminosalicylates and exclusive enteral nutrition (EEN). Corticosteroids are prescribed for moderate patients for induction. Immunomodulators such as azathioprine, 6-MP or MTX are used for maintenance for those.¹⁰

Therapeutic options for Crohn's disease are evolving, and recently, a new treatment approach has been suggested using biological agents to heal mucosa and alter natural history of disease.¹¹⁻¹²

Until now, TNF blockade including adalimumab and infliximab has been prescribed for adult CD patients. In randomized controlled trials, adalimumab rapidly induced and

maintained clinical remission in adults.¹³⁻¹⁷ The efficacy and safety of adalimumab for induction and maintenance of clinical remission in Western children with moderate to severe CD who had failed corticosteroids or immunosuppressants, including prior infliximab in > 40% of subjects, was demonstrated in the Imagine 1 trial.

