The effectiveness assessment of Humira® induction therapy and maintenance therapy will be presented by the number and percentage of the subjects with clinical response. Clinical response is defined as decrease in PCDAI score from baseline by ≥ 15 points and if CDAI score is collected, Clinical response is defined as decrease in CDAI score from baseline by ≥ 70 points.

To investigate the factors affecting the effectiveness, the number and percentage of subjects with clinical response will also be classified by background factors (e.g., demographic factors, treatment factors such as medical history, dosing and administration, concomitant medications, beginning of administration before/after the registration date, etc.) and tabulated. If the effectiveness evaluation of above factors has statistical significance, it will be presented as a separate item.

Statistical Methods

The descriptive statistics for safety and effectiveness parameter in each year will be presented in annual reports.

In final report (Re-examination report), safety and effectiveness outcome by background factor will be summarized and analyzed. The analysis for categorical variables will be performed using chi-square test or fisher's exact test and continuous variables will be performed using Wilcoxon rank sum test or t-test. Also, incidence rate of adverse event collected in overall PMS period will be analyzed and 95% CI will be presented.

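### The 6-month maintenance percentage in section 9.7 counts response against baseline whatever the week-4 status, and only in subjects still treated, so it does not show how many week-4 responses were kept

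*Combined protocol and SAP*

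**What the plan says.** All of this is in the combined protocol and SAP.

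- **Measure (9.7, Effectiveness Analysis).** One summary serves both phases: "The effectiveness assessment of Humira® induction therapy and maintenance therapy will be presented by the number and percentage of the subjects with clinical response".
- **Definition of response (9.7).** For PCDAI: "Clinical response is defined as decrease in PCDAI score from baseline by ≥ 15 points". For CDAI, where collected: "Clinical response is defined as decrease in CDAI score from baseline by ≥ 70 points". Both refer to baseline, and neither refers to the week-4 score.
- **Induction set (9.7, Analysis Population).** Subjects "prescribed Humira® for 4 weeks including induction period (± 1 week) and for whom effectiveness evaluation parameters have been recorded".
- **Maintenance set (9.7, Analysis Population).** Subjects "prescribed Humira® for 6 months (± 4 weeks) and for whom effectiveness evaluation parameters have been recorded". No response, and no score, at week 4 is required.
- **Exclusions (9.7, Analysis Population).** Subjects with missing parameters are left out. So are those who stopped early: "they discontinued administration prior to the effectiveness evaluation will be excluded from the evaluation".
- **Data (9.3, Effectiveness).** PCDAI is collected before treatment, at 4 weeks and at 6 months, and CDAI where possible.

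The plan does not define maintained, lost or late response, and it plans no table of week-4 status against month-6 status. The background factors for the response tables form an open list that does not name week-4 response.

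**The concern.** A percentage headed maintenance effectiveness will be read as the share of induced responses that lasted. The planned figure is something else, for two reasons.

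- **Week-4 status is ignored.** A child who did not respond at week 4 but responded later counts as a maintenance success. Within the month-6 set, a child who responded and lost response looks the same as one who never responded.
- **Discontinuers leave the denominator.** A week-4 responder who stopped before month 6 is removed from the calculation and is not counted as a response that was not kept.

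The week-4 and month-6 percentages can also come from different, overlapping groups, so setting them side by side does not measure retention. At stake is one descriptive statement in the re-examination report: it could present the month-6 percentage as evidence of durability that the planned tables do not supply.

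**Working it through.** The plan states no expected response rate and no precision target for effectiveness, so there is no figure of its own to reproduce. The check asks what the two planned percentages can say about retention. All response rates below are assumptions.

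**1. Same subjects at both visits.** Let p4 and p6 be the response proportions at week 4 and month 6, r the proportion of week-4 responders still in response at month 6 (retention), and l the proportion of week-4 non-responders who respond by month 6 (late response). Then

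p6 = p4 × r + (1 − p4) × l.

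Because l lies between 0 and 1, r lies between max(0, p4 + p6 − 1)/p4 and min(p4, p6)/p4. If week-4 responders are at least as likely as non-responders to respond at month 6 (r ≥ l), the equation also gives r ≥ p6.

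| p4 | p6 | Lower limit, no condition | Lower limit if r ≥ l | Upper limit |
|---|---|---|---|---|
| 60% | 60% | 0.20/0.60 = 33% | 60% | 0.60/0.60 = 100% |
| 70% | 60% | 0.30/0.70 = 43% | 60% | 0.60/0.70 = 86% |
| 50% | 50% | 0/0.50 = 0% | 50% | 0.50/0.50 = 100% |

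The 33% and 43% limits both require l = 1, that is, every week-4 non-responder responds late. The limits under r ≥ l are the more plausible ones, and they are still wide.

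**2. Adding the exclusion of discontinuers.** Take 100 children, of whom 60 respond at week 4. Of those 60, 30 stop before month 6 and 30 continue and stay in response. All 40 non-responders continue, and 12 respond late.

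- Planned induction figure: 60/100 = 60%.
- Planned maintenance figure: (30 + 12)/(30 + 40) = 42/70 = 60%.
- Retention among week-4 responders with both scores: 30/30 = 100%.
- Retention among all week-4 responders, with discontinuation counted as not maintained: 30/60 = 50%.

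The planned pair reads 60% and 60%, while half of the week-4 responses were not shown to be kept. Retention of 50% falls below the 60% limit from step 1, even though responders who continued did better than non-responders (100% against 12/40 = 30%). That limit assumed the same subjects at both visits. The example also shows that a retention rate restricted to subjects with both scores would keep the completer bias.

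**3. Precision of a retention figure.** Section 9.5 expects about 141 subjects, of whom 71 + 31 = 102 start treatment after enrolment and 29 + 10 = 39 before. Clopper-Pearson 95% intervals with an assumed 60% week-4 response and about 70% retention:

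- All 141 with a week-4 score: 141 × 0.60 ≈ 85 responders; 59/85 = 69%, 95% CI 58.5% to 79.0%, about ±10 points.
- Only the 102: 102 × 0.60 ≈ 61 responders; 43/61 = 70%, 95% CI 57.4% to 81.5%, about ±12 points.

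Over assumed week-4 response of 50% to 80% and retention of 60% to 80%, the half-width is about 8 to 12 points with 141 subjects and about 9 to 14 with 102. That is usable for description.

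**The case against.** The strongest reply is that maintenance here names a treatment phase. Both sets are defined by duration of prescription, the calculation is stated openly, and nowhere does the plan pose durability of week-4 response as a question. Section 8.0 sets a safety objective, with effectiveness inside its item on other information and in a general hypothesis of efficacy. Section 9.7 justifies the sample size on detecting adverse events only. This stands, and it keeps the point minor. It does not remove it: if only the phase is meant, the heading maintenance effectiveness still claims more than the figure gives, so the label should change on either reading.

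Three stronger conclusions might be inferred, and the documents do not support them.

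- *The study cannot show whether response was maintained.* The gap is in the planned tables. Section 9.3 collects the scores that would answer the question in subjects who have them.
- *Much of the induced response may have been lost and replaced by late responders.* The plan contains no response rates. The 33% and 43% limits are algebraic extremes that need every week-4 non-responder to respond late.
- *The plan must report remission.* Section 7.0 does say that "the goal of treatment of CD for children is to induce and maintain clinical remission", but as general background; its stated rationale is regulatory compliance and comparison of safety with the label. Preferring remission to response is a choice of endpoint, and the documents give no PCDAI cut-off for it. Remission could be an optional addition, not a required correction.

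**Conclusion.** The point holds as one of labelling and a missing table. The planned month-6 percentage mixes kept responses with late ones and drops subjects who stopped, so it does not measure retention of week-4 response. The PCDAI and CDAI definitions share this feature.

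Its size can only be illustrated. With assumed 60% response at both visits in the same subjects, retention of 60% to 100% fits if week-4 responders do at least as well later as non-responders. Step 2 shows that the exclusion of discontinuers can take it below that range. How far depends on how many week-4 responders stop treatment, which the documents do not give.

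Severity is minor: this is a single-arm descriptive surveillance, and no decision rule rests on the figure.

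**What to change.** In section 9.7:

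1. Keep the month-6 percentage, but label it *response at 6 months among subjects still treated and assessed*.
2. Add a table of week-4 status by month-6 status, with month-6 categories responder, non-responder, discontinued and score missing. State how many subjects lack a week-4 score, separately for the group who started treatment before enrolment.
3. From that table report, with a 95% CI, the proportion of all week-4 responders still in response at month 6. Count discontinuation as not maintained, and show missing scores on their own line so the reader can see how far they could move the figure.
4. Report late response (week-4 non-responders in response at month 6) separately.
5. Apply the same rules to CDAI where it is collected.

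The cost is some SAP wording and one table from scores already collected. The retention figure rests on a smaller denominator and has a wider interval: about ±10 points on 85 responders, against about ±8 for a 60% rate in all 141 (1.96 × √(0.6 × 0.4/141) = 0.081). It will probably also look less favourable than the percentage now planned, because discontinuations count against it.

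### PCDAI is collected as a score at three time points, but section 9.7 specifies only a yes/no response, with no confidence interval and no baseline adjustment in the factor comparisons

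*Combined protocol and SAP*

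**What the plan says.** Section 9.3 (Variables, Effectiveness) collects "the effectiveness data (i.e. PCDAI score) at previous times before Humira® treatment", and again "at 4 weeks (visit window: ± 1 week) and at 6 months (visit window: ± 4 weeks) post-treatment will be collected". A numerical score with a pre-treatment value is therefore on the case report form. CDAI is added where possible.

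Section 9.7 (Effectiveness Analysis) turns this into one outcome: "Clinical response is defined as decrease in PCDAI score from baseline by ≥ 15 points", with a fall of at least 70 points as the CDAI counterpart. Results for induction and maintenance "will be presented by the number and percentage of the subjects with clinical response". For factors affecting effectiveness, "the number and percentage of subjects with clinical response will also be classified by background factors", and factors reaching statistical significance are reported as a separate item.

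Two general sentences under Statistical Methods in 9.7 bear on the point. One is "The descriptive statistics for safety and effectiveness parameter in each year will be presented in annual reports". The other says that, in the final report, "continuous variables will be performed using Wilcoxon rank sum test or t-test". Neither names PCDAI. The only 95% CI in 9.7 is for the incidence of adverse events.

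**The concern.** The hypothesis in section 8.0 says that Humira will be efficacious as well as safe, and 9.7 goes beyond description by testing background factors against effectiveness. For those tests the plan names only the dichotomised outcome. A fall of 14 points and no fall at all count the same, as do falls of 15 and 40.

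The chance of falling by 15 points also depends on the starting score; at the extreme, a subject who starts below 15 cannot respond. If a factor such as prior therapy or concomitant steroids goes with disease severity, an unadjusted comparison of response rates mixes the factor with the starting score. The baseline PCDAI needed to separate them is already collected.

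At stake are the power and interpretability of the factor comparisons, and whether a reader of the final report can see how precise the response percentage is and how far scores moved.

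**Working it through.** **1. The plan's own figure.** The only statistical design calculation is in 9.7 and concerns safety. With 600 subjects and an event rate of 0.5%, the expected count is 600 × 0.005 = 3, and the chance of at least one event is 1 − e⁻³ = 1 − 0.0498 = 0.9502. It reproduces. There is no corresponding figure for effectiveness: no expected response rate, no SD of PCDAI change and no distribution. Everything in steps 2 to 5 therefore rests on stated assumptions.

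**2. Information kept by the yes/no comparison, normal change.** For detecting a shift in score between two groups, the efficiency of comparing response rates relative to comparing means is RE(p) = φ(z_p)² / [p(1 − p)], with p the response rate.

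| Response rate (assumed) | φ(z_p) | RE | Loss | 141 × RE |
|---|---|---|---|---|
| 50% | 0.3989 | 0.1592/0.25 = 0.637 | 36% | 89.8 |
| 70% | 0.3477 | 0.1209/0.21 = 0.576 | 42% | 81.2 |
| 80% | 0.2800 | 0.0784/0.16 = 0.490 | 51% | 69.1 |
| 90% | 0.1755 | 0.0308/0.09 = 0.342 | 66% | 48.3 |

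The last column takes all 141 as evaluable. The effectiveness sets in 9.7 leave out subjects with missing evaluations or who stopped before the evaluation, so the real number is at or below 141.

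**3. Sensitivity to shape.** In general RE = f(q_p)² σ² / [p(1 − p)], where f is the density of the change, q_p its p-quantile and σ² its variance.

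- Logistic (σ² = 3.290): 0.25² × 3.290/0.25 = 0.822 at 50%, and 0.16² × 3.290/0.16 = 0.526 at 80%. Losses are 18% and 47%.
- t with 5 df (σ² = 1.667): 0.3796² × 1.667/0.25 = 0.961 at 50%, and 0.2376² × 1.667/0.16 = 0.588 at 80%. Losses are 4% and 41%.

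Between 50% and 80% response, these heavier tails make the loss smaller than under normality.

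**4. Illustration with a factor the plan names.** Section 9.7 lists starting Humira before or after registration. Table 2 in 9.5 gives 29 + 10 = 39 before and 71 + 31 = 102 after. Assume a true difference of 0.5 SD, a normal change and two-sided alpha 0.05 (the plan states no alpha).

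- On the score: the standard error in SD units is √(1/39 + 1/102) = 0.188, so power is Φ(0.5/0.188 − 1.96) = Φ(0.70), about 76%.
- On response: with rate p in the larger group, the smaller group has Φ(z_p ± 0.5). Power is Φ[(d − 1.96 se₀)/se₁], where d is the difference in rates and se₀ and se₁ are its pooled and unpooled standard errors.
  - Smaller group does worse: 50% v 30.9%, 54%; 65% v 45.4%, 56%; 80% v 63.4%, 53%.
  - Smaller group does better: 65% v 81.2%, 46%; 80% v 91.0%, 32%.

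Power on response is thus about 32% to 56%, against 76% on the score.

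**5. Precision the response percentage would show.** The approximate 95% half-width is 1.96 √[p(1 − p)/141]: 8.3 percentage points at 50% response and 6.6 at 80%. It is wider with fewer evaluable subjects. The plan does not say this interval will be reported.

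**The case against.** **The calculation does not touch the main effectiveness result.** That result is a single-arm response percentage. Reporting it loses nothing against its own target, and a mean change answers a different question. A predefined responder rate suits a non-interventional surveillance whose objective is safety. This stands, and so does its corollary: there is no ground for demoting the responder percentage.

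**The general sentences might already cover the score.** A reader might infer from 9.7 that the score is never to be analysed. The documents do not support so strong a statement, because the sentences on descriptive statistics and on tests for continuous variables could be read to include PCDAI. They could equally mean continuous background factors such as age. They do not name PCDAI, give it an interval or adjust for baseline. The supportable statement is that no continuous PCDAI analysis is specified.

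**The efficiency loss is not a property of this study.** It is tempting to say the plan discards 36% to 51% of the information. That holds only for a normal change with 50% to 80% response, and the documents give neither. With an extremely heavy-tailed change (double exponential) at 50% response, the yes/no comparison would even beat the mean (RE = 2.0). This stands, so any figure must carry its assumptions.

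**The reduction from 600 to 141 is not lost effectiveness power.** A reader might link the two. The 600 was set to detect a 0.5% serious adverse event, and the 141 reflects feasible recruitment. Neither was set for effectiveness.

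**Few subjects may start below 15.** Section 7.0 describes moderate to severe disease, and 9.5 describes the label as confined to severely active disease. Section 9.2 sets no minimum PCDAI of its own, but nothing shows that an appreciable number would be unable to respond. The case for baseline adjustment does not need such subjects; it needs only that the chance of a 15-point fall varies with the starting score.

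**Conclusion.** The point holds as a low-cost improvement, not as an error that invalidates the plan. Section 9.7 specifies no continuous PCDAI analysis for a score collected at three time points, compares background factors on an unadjusted yes/no outcome, and promises no 95% CI for the response percentage.

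The loss falls on the factor comparisons. Assuming a near-normal change and 50% to 80% response, they keep about 64% to 49% of the information on a shift in score, so 141 evaluable subjects would be worth about 90 to 69. Over the other cases in the table and the logistic and t sensitivities, the loss runs from 4% (t with 5 df, 50% response) to 66% (normal, 90% response). The missing interval and the missing baseline adjustment need no distributional assumption.

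**What to change.** In section 9.7:

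- Keep the responder percentage as planned, and add its 95% CI at 4 weeks and 6 months.
- Add mean PCDAI and mean change from baseline at 4 weeks and 6 months, each with SD and 95% CI.
- For the background-factor comparisons, add a linear model of PCDAI at the visit with baseline PCDAI as covariate, shown alongside the responder tables.

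The cost is SAP wording and a few more tables; all the data are already collected. The change does not address the exclusion of subjects with missing evaluations or early discontinuation, which affects a mean change as much as a response percentage. The number evaluable should therefore stand beside each estimate.
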